3.5 Subject Adjunct Products to be Used in the Study

The Test and Control lenses are designed for frequent replacement.

Johnson & Johnson Blink RevitaLens® Multipurpose Disinfecting Solution will be the primary multi-purpose lens care system for this study. Alcon Clear Care® Cleaning and Disinfection Solution will be used as an alternative for those subjects who have a history of, or present with, sensitivities or reduced wearing times associated with chemically preserved multi-purpose lens care systems. Subjects may be switched from Johnson & Johnson Blink RevitaLens® Multipurpose Disinfecting Solution to the Alcon Clear Care® Cleaning and Disinfection Solution, if required due to symptoms. Menicon LacriPure will be dispensed at the licensed investigators discretion to be used as a rinsing solution following disinfection with Alcon Clear Care® and prior to lens insertion. Minor solution related symptoms or subjective findings do not qualify as an adverse event unless accompanied by the presence of a grade 3 or greater slit lamp finding.

Investigational Sites will be provided with Eye-Cept, a non-preserved single dose rewetting drops containing an aqueous solution of sodium chloride and boric acid. Eye-Cept Rewetting Drops are the **only** rewetting drops that may be used by study subjects.

The use of over-the-counter (OTC) artificial tears while wearing lenses is prohibited in this study.

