5.6 Equipment Used for Assessments

Each site must have the maintenance records (both preventive and equipment failure) and where appropriate the calibration records (**within the last 12 months**) for equipment used to perform standard ophthalmic examinations. This includes but is not limited to:

- Phoropter (manual or automatic) or trial lens frame and lenses.
- Snellen Visual Acuity Charts calibrated for the appropriate test distance.
**
- Keratometer (manual or automatic) – topography or corneal mapping equipment may be used for assessing keratometric measurements as long as the same instrument and function are used for all subjects at all visits.
**
- Lensometer: (manual or automatic) **

- Slit Lamp Biomicroscope or Videoscope
 - ** Calibrations records required to be maintained in Investigational Site files.

Grading scales for recording the observations are provided in Appendix E.

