5.10.4 Ocular Health Assessment Exclusion Criteria

Does the subject have

1. Clinically significant (grade 2, 3 or 4) anterior segment abnormalities; or the presence of any infection of the eye, lids, or associated structures.
2. Pathological dry eye or associated dry eye symptoms with decreased tear levels and punctuate staining \geq Grade 2
3. Pterygium
4. Corneal scars within the visual axis
5. Neovascularization or ghost vessels \geq 1.0 mm in from the limbus
6. Giant papillary conjunctivitis of \geq Grade 2
7. Any inflammations such as anterior uveitis or iritis
8. Seborrheic eczema, seborrheic conjunctivitis or blepharitis

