8.2 Sample Size Justification

The completed subjects sample size for this study is planned to be 50 Test Lens subjects and 25 Control Lens subjects based on a two to one (2:1) ratio of Test Lens subjects to Control Lens subjects.

The sample size for this study is based on the ISO 11980:2012 Ophthalmic optics – Contact lenses and contact lens care products – Guidance for clinical investigations.

Expected drop-out rates for both the Test and the Control lenses are calculated to be approximately 15%.

Due to the limited sample sizes required for this study the power calculations and level of significance are not appropriate for calculation. Differences between the results for the Test and Control cohorts will be evaluated based on clinical judgments.

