8.3 Analysis & Procedures

Throughout the analysis of data, the results for each patient/eye will be used when available for summarization and analysis. All subject data will be considered for evaluation unless a significant protocol deviation was reported. Written justification will be required for the use of data in the evaluation of the safety and/or efficacy of study product from any subject or investigational site found to have a significant protocol deviation.

Summary analysis for all dispensed subjects will be presented, including completed and discontinued subsets of the Test and Control populations.

Descriptive statistics will be reported by cohort at baseline, fitting and follow-up. Continuous variables will be summarized using sample size (N), mean, standard deviation (SD), minimum and maximum, and categorical data variables will be summarized using the sample size, frequency distribution (count and percentage of subjects or eyes in each category), mean and standard deviation.

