8.4 Primary Safety Endpoint

The primary safety endpoints will be a comparison of the slit lamp findings and adverse events reported as associated with the Test lenses with those same findings reported as associated with the Control lenses by all scheduled and unscheduled follow-up visits. Slit lamp findings [REDACTED] are the primary indicators of safety issues with contact lenses.

[REDACTED]

Analysis of the results of the study will be based on a comparison of the differences in rates and degree of slit lamp findings between the Test and the Control lenses and the application of a clinical significance determination against the results. Clinical significance will be established through the average severity of the findings reported.

It is expected that the frequency and severity of the slit lamp findings and adverse events will be substantially equivalent between the Test and the Control lenses.

The following slit lamp findings will be presented and the frequency and average severity of findings by visit will be assessed.

- Epithelial Edema
- Stromal Edema
- Corneal Infiltrates
- Corneal Vascularization
- Corneal Staining
- Limbal Hyperemia
- Bulbar Hyperemia
- Palpebral Conjunctivitis
- Other Slit Lamp Findings

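### In the visible text of 8.4, average severity is the only stated criterion for clinical significance of slit lamp findings, and a mean grade can hide high grades that occur only with the Test lens

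*Combined protocol and SAP*

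**What the plan says.** Section 8.4 makes slit lamp findings and adverse events the primary safety endpoints. For slit lamp findings it plans a "comparison of the differences in rates and degree of slit lamp findings between the Test and the Control lenses" and then applies a clinical significance determination. The next sentence defines that determination: "Clinical significance will be established through the average severity of the findings reported". Of the listed findings, it says that "the frequency and average severity of findings by visit will be assessed". The visible text names no maximum grade, no proportion at or above a grade and no denominator for the average.

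Four other places bear on this:

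- Section 8.3 summarizes categorical variables by "count and percentage of subjects or eyes in each category", together with a mean and standard deviation.
- Section 8.2 sets aside power and significance level; differences between the cohorts "will be evaluated based on clinical judgments".
- Section 5.10.4 excludes at entry "Clinically significant (grade 2, 3 or 4) anterior segment abnormalities". Section 3.5 says that minor solution-related symptoms are not adverse events "unless accompanied by the presence of a grade 3 or greater slit lamp finding". Neither place is presented as an outcome threshold.
- Section 5.6 states: "Grading scales for recording the observations are provided in Appendix E". That appendix is not in the public text. Part of 8.4 is redacted, and 5.4.1 and 8.6.1 are not shown.

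**The concern.** Slit lamp grades are ordinal, and for safety the upper end of the scale matters most. An average gives a few high grades little weight and can be pulled down by the number of low grades or of clear eyes. With no significance level and no margin, the sentence in 8.4 is the only visible guide to how the clinical judgment on slit lamp findings should be made. Taken literally, it could support a conclusion of substantial equivalence when the more serious findings are confined to one lens. Because the denominator is open, it could also support opposite conclusions from the same data.

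**Working it through.** **Inputs.** Section 8.2 plans 50 Test and 25 Control completers. With two eyes each, that is 100 Test eyes and 50 Control eyes. The plan gives no figure for severity, so none can be reproduced. The sample size is coherent: at about 15% drop-out, 50/0.85 = 58.8 and 25/0.85 = 29.4, against the 60 and 30 dispensed subjects in 5.10. Whole grades 0 to 4 are assumed, and all grade counts below are illustrative.

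**Formulas.** Let S be the sum of grades.
- Mean over all eyes = S / number of eyes. This equals P(grade ≥1) + P(≥2) + P(≥3) + P(≥4).
- Mean over findings = S / number of eyes with a finding.

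**A. Mean over all eyes.**

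| | Test (100 eyes) | Control (50 eyes) |
|---|---|---|
| Grade 1 | 8 | 12 |
| Grade 3 | 4 | 0 |
| S | 8×1 + 4×3 = 20 | 12×1 = 12 |
| Mean over all eyes | 20/100 = 0.20 | 12/50 = 0.24 |
| Any finding | 12/100 = 12% | 12/50 = 24% |
| Grade 2 or higher | 4% | 0% |
| Grade 3 or higher | 4% | 0% |

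Check by the second form: Test 0.12 + 0.04 + 0.04 = 0.20; Control 0.24. The four grade 3 eyes add 4×3/100 = 0.12 to the Test mean. Test has 8% of eyes at grade 1 against 24% in Control, which takes off 0.16. Both the rate and the mean favour Test, although every finding above grade 1 is in Test.

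**B. Same data, mean over findings.** Test 20/12 = 1.67; Control 12/12 = 1.00. The ranking reverses, so the undefined denominator decides the answer.

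**C. Dilution in the mean over findings.** Take Test with 4 grade 1 and 4 grade 3: (4 + 12)/8 = 2.00. Add 36 grade 1 eyes: (40 + 12)/44 = 1.18. Four eyes are still at grade 3, but the measured severity has fallen. Control with 6 grade 1 and 1 grade 2 gives 8/7 = 1.14, so the arms look alike. The added findings do raise the Test rate from 8% to 44%, against 7/50 = 14% in Control, and 8.4 compares rates. This route also needs Control to have some findings above grade 1; otherwise its mean is exactly 1 and Test cannot match it.

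**D. Precision of a count.** Four grade 3 eyes lie in 2 to 4 Test subjects. Newcombe 95% intervals for the difference are:
- 2/50 against 0/25: 4.0 points (-9.6 to 13.5)
- 4/50 against 0/25: 8.0 points (-6.2 to 18.8)

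**The case against.** The strongest reply is that high grades would not go unseen. Section 8.3 gives counts per category (if grades are treated as categorical), 8.4 also compares rates and adverse events, 8.7.5 puts all data into tables or listings, and 8.2 leaves the decision to clinical judgment. This stands and limits the harm. It does not repair the stated criterion: in example A the tables would show 4 against 0 while a mean over all eyes points the other way.

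A second reply is that masking needs either a visible excess of findings in Test or a true Test advantage at grade 2 or higher. This is right in part. Dilution by added grade 1 findings affects only the mean over findings, and it raises the rate. At equal finding rates, with grade 3 or higher only in Test, the Test mean can be no higher only if Control has more eyes at grade 2 or higher. As a general rule the reply fails: in example A Test has the lower finding rate and the worse result at both grade 2 and grade 3.

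A third reply is that a threshold may stand in the redacted part of 8.4, in 5.4.1 or 8.6.1, or in Appendix E. That cannot be excluded, so the point is confined to the visible text.

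**Conclusion.** The point holds as a weakness of the stated criterion, not of the data collected. In the visible text of 8.4, clinical significance rests on average severity alone, without a denominator. Over all eyes, that average can favour Test (0.20 against 0.24) when grade 2 or higher and grade 3 or higher are both 4% against 0%. The size depends on assumed counts. The examples show that the mean can mislead, not that it is likely to here.

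A reader might infer more, and the documents do not support it:

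- That the plan has no threshold at all. Hidden text may contain one.
- That mild findings dilute serious ones under any denominator. Within an arm, an added grade 1 eye that would otherwise be clear raises the mean over all eyes.
- That 5.10.4 and 3.5 contradict 8.4. They serve eligibility and the adverse event status of solution-related symptoms.
- That a grade 3 excess must override everything else. The visible text does not support so fixed a rule; the counts inform a judgment.

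**What to change.** Replace the sentence in 8.4 with text such as: *The clinical significance determination will be based on the distribution of grades: the number and percentage of subjects (worst eye, all post-dispensing visits), and of eyes by visit, at or above grade 2 and at or above grade 3, by assigned lens and for each finding, considered alongside adverse events. Mean grade will be given as a descriptive summary with its denominator stated.*

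The sponsor should confirm both cut-offs as outcome thresholds against the Appendix E scales. If the hidden text already sets a threshold, 8.4 should refer to it in place of the average.

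The cost is a few sentences and one table from data already collected. The downside is that high-grade counts will be small and imprecise, as the intervals in D show, and will still need clinical judgment.

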6.4.1 Reasons For Exit

0. Study Completed

Possible reasons for discontinuation include:

1. Screen Failure – the subject does not meet the protocol specified inclusion criteria or has one or more of the exclusion criteria present.
 - 1.1. Previous History
 - 1.2. Refractive Assessment
 - 1.3. Ocular Health Assessment
 - 1.4. Trial Lens Fitting
 - 1.5. Trial Lens VA
 - 1.6. Trial Lens Comfort
 - 1.7. Subject was unable to insert/remove lenses or use care system
 - 1.8. Licensed Investigator Decision
 - 1.9. Subject Decision
2. Unacceptable Lens Fit – the subject is exited from the study due to an unacceptable lens fit at a visit following dispensing.
3. Unacceptable Visual Acuity – the subject is unable to obtain or maintain acceptable visual acuity with the study lenses at a visit following dispensing.
4. Unacceptable Lens Comfort – the subject is exited from the study for comfort reasons at a visit following dispensing.
5. Objective Ocular Findings – the subject has been exited from the study due to objective ocular findings that are not specifically cited as adverse events. The reason for discontinuation should indicate the relationship (related, unrelated or unknown) of the findings to the study lenses. The reason for discontinuation must be recorded in the comments section of the Exit Form.

6. Adverse Event – the subject has been reported to have an adverse event and was discontinued due to the adverse event.
7. Other: Subject Decision – the subject decides for reasons other than those listed to exit from the study. The reason must be recorded in the comments section of the Exit form.
8. Other: Licensed investigator, sponsor or IRB Decision – the subject is exited from the study based on a decision by the licensed investigator, the Sponsor or the reviewing IRB. The reason for discontinuation must be recorded in the comments section of the Exit Form.
9. Protocol Deviation – the subject or the investigational site is repeatedly found to be in deviation of the study protocol.

NOTE: Subjects who become **pregnant** while enrolled in the study must notify a licensed investigator and be discontinued from the study as a **Protocol Deviation**.

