8.7.6 Treatment of Missing, Unused or Spurious Data

The analysis set will be the full analysis set, which consists of all subjects randomized into the study with an actual lens dispensed. Discontinued subject data will be analyzed separately from the completed subject data.

Missing data will be accounted for in the sample size accounting.

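### Slit lamp safety is shown visit by visit, with no visible rate of dispensed subjects who ever had a finding, so a Test excess spread over five visits can look small at each

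*Combined protocol and SAP*

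**What the plan says.** Section 8.4 makes slit lamp findings and adverse events the primary safety endpoints, compared "by all scheduled and unscheduled follow-up visits". The slit lamp analysis is described as a "comparison of the differences in rates and degree of slit lamp findings between the Test and the Control lenses", and the decision rule is that "Clinical significance will be established through the average severity of the findings reported". For the listed signs, the display is specified in one clause: "the frequency and average severity of findings by visit will be assessed".

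The handling of subjects who leave is spread over several sections:

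- **8.3:** "the results for each patient/eye will be used when available for summarization and analysis", and "Summary analysis for all dispensed subjects will be presented, including completed and discontinued subsets of the Test and Control populations".
- **8.7.6:** discontinued and completed subjects are analysed separately, and "Missing data will be accounted for in the sample size accounting".
- **6.4.1, reason 5:** this covers the case where "the subject has been exited from the study due to objective ocular findings that are not specifically cited as adverse events". Reason 6 covers exit for an adverse event.
- **6.4.2 and 6.4.3:** a full examination is due on the exit date, and a subject who stops the lens for an adverse event or ocular finding is followed until the condition resolves, returns to its pre-study state or is judged permanent.
- **6.3.2:** a visit attended without lenses is classed as unscheduled.

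Section 8.2 sets no significance level or power and leaves differences between the arms to clinical judgment.

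**The concern.** Because there is no test and no margin, the tables themselves are the evidence for substantial equivalence. A by-visit table shows how many subjects had a finding on each occasion. It does not show how many of those given the lens ever had one, which is the natural safety question for a three-month comparison.

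The two can differ widely when findings are uncommon and scattered over time. A subject who exits for a finding counts at the visit where it was seen and then contributes nothing to later scheduled-visit rates. Nor can the per-subject figure be recovered by adding the visits, because by-visit frequencies do not separate new findings from repeated ones.

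The other planned displays do not clearly fill the gap. Reason 5 exits are by definition outside the adverse events. The completed subset excludes everyone who exited, and a discontinued subset has discontinued subjects as its base. What is at stake is a primary safety comparison that looks balanced at every visit although clearly more Test subjects had a finding.

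**Working it through.** **Inputs from the plan.** About 60 Test and 30 Control subjects dispensed (5.10); 50 and 25 completers and about 15% drop-out (8.2); five scheduled follow-up visits (6.3). No finding rate is given, so every count and rate of findings below is an assumption.

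**The plan's own figure.** Inflating completers by 1/(1 − 0.15): 50/0.85 = 58.8, so 59; 25/0.85 = 29.4, so 30; total 89 against 90 stated. The sample size reproduces.

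**Illustration with assumed counts.** At each scheduled visit, 2 further Test subjects have a grade 2 or higher finding and exit. Control has 1 such subject in total, at Week 1.

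| Visit | Test | Control |
|---|---|---|
| Week 1 | 2/60 = 3.3% | 1/30 = 3.3% |
| Week 2 | 2/58 = 3.4% | 0 |
| Month 1 | 2/56 = 3.6% | 0 |
| Month 2 | 2/54 = 3.7% | 0 |
| Month 3 | 2/52 = 3.8% | 0 |
| Ever, per dispensed subject | 10/60 = 16.7% | 1/30 = 3.3% |

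The largest gap at any visit is 3.8 points; the per-subject gap is 16.7 − 3.3 = 13.3 points (from unrounded rates). Ten exits leave 50 Test completers, which does not fall below the threshold of 50 in 8.7.9.

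**Where the dilution comes from.** If the denominator stayed at 60, each visit would show 2/60 = 3.3%. Losing the exited subjects raises the later rates slightly, to 3.8%. So the shrinking denominator does not hide the excess; splitting 10 first findings over five tables does. Exit matters in another way: had the findings persisted in subjects who stayed, the Month 3 rate would have built up to 10/60.

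**Average severity.** Suppose instead 9 Test subjects (15% of 60) exit with a grade 3 finding, spread 2, 2, 2, 2, 1 over the visits, and everyone else is grade 0. The by-visit Test mean grade is then 3 × 2/60 = 0.10 at Week 1, 3 × 2/54 = 0.11 at Month 2 and 3 × 1/52 = 0.06 at Month 3. Per subject this is 9/60 = 15.0%.

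**Simulation.** This used 60 against 30 subjects, five visits, a constant new-finding rate per visit, every finding leading to exit, and 40,000 runs. The cumulative rate is 1 − (1 − h)^5. The last two columns give the chance of seeing a Test excess of 10 points or more, a yardstick chosen only for illustration.

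| New findings per visit, Test v Control | Cumulative | At any single visit | In the cumulative table |
|---|---|---|---|
| 2% v 1% | 9.6% v 4.9% | 0.4% | 20% |
| 3% v 1% | 14.1% v 4.9% | 3% | 48% |
| 4% v 1% | 18.5% v 4.9% | 10% | 73% |
| 5% v 1% | 22.6% v 4.9% | 23% | 89% |

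**What a cumulative table cannot do.** Fisher's exact test gives p = 0.09 for 10/60 against 1/30 and p = 0.16 for 9/60 against 1/30. At 3% v 1% per visit it reaches p < 0.05 in about 17% of runs.

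**The case against.** The strongest reply is that the plan does not lose these subjects. They have an exit examination and are followed afterwards. Their lens-free visits count as unscheduled, and unscheduled visits are part of the primary safety comparison. They also appear in the discontinued summary, under their exit reason and, where it applies, among the adverse events, while 8.7.5 puts all data into tables or listings. A reader might infer that subjects who exit for a finding vanish from every later table. The documents do not support that; only the later scheduled-visit rates lose them. Even the by-visit denominator is inferred from the by-visit wording and the use of data when available, because the plan does not state it.

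Second, the sentence on differences in rates and degree is not limited to visits, so it could be read to cover an overall rate. It could, but it gives neither a denominator nor a time frame.

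Third, parts of 8.4 are redacted, the safety endpoint text before 5.4.2 is not supplied, and 8.6.1 (Secondary Safety Endpoints) appears in the contents without its body. A cumulative summary may stand there. This limit is real.

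Fourth, the illustration is favourable to the point. No visible text says that every finding leads to exit, and an alert reader would see Test findings at five visits out of five and a cluster of finding-related exits. That is fair: the signal could be pieced together. It does not follow that the reader will be shown it as a rate.

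**Conclusion.** The point holds as a gap in the visible text. Slit lamp findings are compared by visit, and no display gives a rate per dispensed subject. Under the assumed counts, a 13.3-point per-subject difference never exceeds 3.8 points at a visit. Under assumed rates of 3% v 1% per visit, a 10-point excess shows at some visit in about 3% of trials, against 48% in a cumulative table. These sizes rest on assumed finding rates, an even spread over visits and exit after every finding.

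Two stronger readings should be resisted. One is that informative exit by itself hides the harm; the arithmetic shows that splitting over visits does most of it. The other is that the plan would wrongly establish equivalence. It has no formal criterion, and even the cumulative table would be inconclusive as a test at 60 against 30. The conclusion is subject to what the redacted and unsupplied safety text contains. This is an inexpensive improvement that should be made, not a fatal flaw.

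**What to change.** Add to 8.4 one descriptive per-subject table by arm, with all dispensed subjects as the denominator:

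- For each listed sign and for any sign, the number and percentage with at least one finding of grade 2 or higher (the level that 5.10.4 treats as clinically significant for eligibility), and the distribution of the worst grade in either eye.
- Coverage of all scheduled, unscheduled and exit examinations from dispensing to exit, including findings first seen after a lens was removed. Restricting it to examinations on the lens could drop a subject who took the lens out because of symptoms.
- The number exited under reason 5 and under reason 6.
- Confidence intervals for the rates and for the difference, with no hypothesis test.

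Keep the by-visit tables, which show timing, and state their denominator. If redacted text already specifies such a summary, a cross-reference in 8.4 is enough. The grade 2 cut should be checked against the grading scales in Appendix E, which are not in the supplied text.

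The cost is one table from data already collected and two or three sentences in 8.4. A cumulative rate does not show when findings occur, which is why the by-visit tables stay.
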